1.4. Sample Size Determination

Approximately 160 patients will be enrolled in this study, with a 3:1 randomization ratio to either vutrisiran or patisiran.

The sample size was chosen to enable an adequate characterization of the long-term safety profile, as well as the efficacy of vutrisiran in this patient population. For the primary efficacy endpoint of mNIS+7 and the secondary endpoint of Norfolk QoL-DN total score, the vutrisiran group in the Phase 3 study will be compared to the placebo group from the APOLLO study. For the mNIS+7 change from baseline at 9 months, the observed mean (\pm standard deviation [SD]) was 15 ± 17 points for the placebo group from the APOLLO study. Assuming a mean change of 0 points for the vutrisiran group, there is $>90\%$ power to establish the superiority over placebo using a 2-sided t-test with a significance level of 0.05. For the Norfolk-QoL DN total score change from baseline at 9 months, the observed mean (\pm SD) was 11.5 ± 19.2 points for the placebo group from the APOLLO study. Assuming a mean change of -4 points for the vutrisiran group, there is $>90\%$ power to establish the superiority over placebo using a 2-sided t-test with a significance level of 0.05.

For safety, a sample size of >100 patients on vutrisiran can provide reasonable assurance that the true cumulative one-year incidence of adverse drug events (ADE) is no greater than 3% when no ADE is observed.

To match the cardiac disease severity with the APOLLO study population, the study plans to enroll no more than 15% of patients with baseline NT-proBNP values greater than 3000 ng/L.

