4.4.1.1. ANCOVA/MI

ANCOVA incorporating MI will be the default analysis for most continuous efficacy endpoints at Month 9.

MI is a broadly applicable technique for handling missing data. Missing data are imputed multiple times using a regression method. Each imputed data set is analyzed using the same analysis model, and the point estimates and standard errors are combined to provide inferences that reflect the uncertainty about the missing values. MI assumes the data are missing at random (MAR).

For a given endpoint, missing endpoint values will be multiply imputed separately for each treatment group using a regression procedure, with baseline information including baseline score and KPS as covariates and genotype, age at hATTR symptom onset, prior tetramer stabilizer use, region, FAP stage (I vs. II/III), Cardiac subpopulation, sex, and baseline NIS (<50 vs. ≥50) as factors. For NIS-related endpoints, the categorical baseline NIS score will not be included in the regression procedure.

One hundred imputed datasets (per treatment group) will be generated from the MI regression procedure using SAS PROC MI. Each of the imputed datasets will then be analyzed using an ANCOVA model, including a covariate (baseline value) and factors (treatment group; genotype; age of disease onset, baseline NIS score [<50 vs ≥ 50]), unless otherwise specified. For NIS-related endpoints, the categorical baseline NIS score will not be included in the model.

The resulting estimates (LS mean differences and standard errors) from the 100 imputed datasets will be combined using SAS PROC MIANALYZE to produce inferential results (difference in LS means, 95% CI for the difference, and the P value from the test that the difference is zero). [Rubin 1996] Combined LS mean estimates will be calculated as the average of the 100 complete-data estimates. A total variance estimate will be calculated as a weighted sum of within-imputation variance, which is the average of the complete-data variance estimates, and a between-imputation variance term. Complete details may be found in the SAS documentation for the MIANALYZE procedure (see Combining Inferences from Imputed Data Sets under Details: <http://support.sas.com/documentation/onlinedoc/stat/131/mianalyze.pdf>).

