4.4.1.2. MMRM

MMRM will be the default analysis for most continuous efficacy endpoints at Month 18. MMRM makes use of fully and partially observed data sequences from individual patients by estimating the covariance between data from different time points. The MMRM will be implemented using an unstructured approach to modeling both the treatment-by-time means and the (co)variances, leading to what is essentially a multivariate normal model wherein treatment group means at the primary time point are adjusted to reflect both the actually observed data and the projected outcomes from the patients with missing data. MMRM also assumes data are missing at random (MAR).

For most endpoints, the MMRM will include a covariate (baseline value), factors (treatment group; visit [Month 9; Month 18]; genotype; age of disease onset; baseline NIS score [<50 vs ≥ 50]), and an interaction term (treatment group by visit), unless otherwise specified. For NIS-related endpoints, the categorical baseline NIS score will not be included in the model.

LS mean and mean difference estimates, SEs, 95% CIs, and p-values at Month 9 and Month 18 will be presented.

An unstructured covariance structure will be used to model the within-patient errors. If the model fails to converge, the following covariance structures will be specified in sequence and the first to converge will be used:

1. Toeplitz
2. First order autoregressive
3. Compound symmetry

The Satterthwaite approximation will be used to estimate the degrees of freedom.

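### The placebo comparisons assume one residual variance (ANCOVA) or covariance matrix (MMRM) for two groups from different trials, and no planned analysis relaxes this; the SAP does not fix the direction or size of any resulting error

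*SAP*

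**What the plan says.** All references are to SAP Amendment 3.

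- **Groups (Section 4.4).** Except for TTR, the models contain only vutrisiran from this trial and placebo from APOLLO.
- **Month 9 (Section 4.4.1.1).** "missing endpoint values will be multiply imputed separately for each treatment group". Each completed dataset then goes into an ANCOVA with baseline value, treatment group, genotype, age of disease onset and, except for NIS-related endpoints, baseline NIS category. Neither a group-specific variance nor a robust standard error is mentioned.
- **Month 18 (Section 4.4.1.2).** "An unstructured covariance structure will be used to model the within-patient errors". Toeplitz, first-order autoregressive and compound symmetry follow as fallbacks, with Satterthwaite degrees of freedom. No grouping of the matrix by treatment or study is given.
- **Sample size (Section 1.4).** "Approximately 160 patients will be enrolled in this study, with a 3:1 randomization ratio to either vutrisiran or patisiran". The SDs given are for APOLLO placebo: "17 points for the placebo group from the APOLLO study" for mNIS+7 and "19.2 points for the placebo group from the APOLLO study" for Norfolk QoL-DN. For vutrisiran only means are assumed: "Assuming a mean change of 0 points for the vutrisiran group" and "Assuming a mean change of -4 points for the vutrisiran group". The size of the placebo group is not given.

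**The concern.** In a randomised comparison a common residual variance is a conventional default. Here the two groups were recruited in different trials, and nothing in the SAP argues that their residual spread is equal. The imputation step lets spread differ by group; the analysis step then removes that allowance.

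A pooled variance is weighted towards the larger group, whereas the true variance of the difference depends most on the smaller group. When sizes and variances both differ, the model-based standard error is therefore wrong, and the sign of the error depends on which group is the more variable. Satterthwaite degrees of freedom do not correct this, because they take the fitted common matrix as given.

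At stake are the intervals and p-values for every comparison with placebo: steps 1 to 8 of the US/Japan/Brazil hierarchy (Section 1.3.1) and steps 1 to 5 of the EU/other hierarchy (Section 1.3.2). The TTR step uses a Hodges-Lehmann method against patisiran and is not affected.

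**Working it through.** **1. Inputs.** From Section 1.4: about 160 patients at 3:1, so 160 × 3/4 = 120 on vutrisiran; placebo SD 17 (mNIS+7) and 19.2 (Norfolk); planned differences 15 − 0 = 15 and 11.5 − (−4) = 15.5. Not in the SAP, so assumed: placebo n (60 to 100, with 120 and 150 for contrast) and the vutrisiran/placebo SD ratio (0.7 to 1.2).

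**2. The plan's own figure.** With a common SD, SE = SD × √(1/120 + 1/n). At placebo n = 60:
- mNIS+7: SE 2.69, 15/2.69 = 5.58, power 99.98%.
- Norfolk: SE 3.04, 15.5/3.04 = 5.11, power 99.91%.

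Power exceeds 90% once placebo n reaches 16 (mNIS+7) or 19 (Norfolk). The stated power above 90% reproduces.

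**3. Effect of pooling.** With s_v and s_p the vutrisiran and placebo SDs:
- pooled variance = [119·s_v² + (n − 1)·s_p²] / (118 + n)
- pooled SE = √[pooled variance × (1/120 + 1/n)]
- true SE = √(s_v²/120 + s_p²/n)
- true two-sided error = 2 × [1 − Φ(1.96 × pooled SE / true SE)]

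Worked case, ratio 0.7 and n = 60: s_v = 0.7 × 17 = 11.9; pooled variance = (119 × 141.61 + 59 × 289)/178 = 190.5; pooled SE 2.18; true SE 2.45; SE ratio 0.891; error 8.1%. The 95% half-width is 4.28 where 4.80 is needed.

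True two-sided error by placebo n:

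| SD ratio (vutrisiran/placebo) | 60 | 80 | 100 | 120 | 150 |
|---|---|---|---|---|---|
| 0.7 | 8.1% | 6.7% | 5.8% | 5.0% | 4.2% |
| 0.8 | 6.9% | 6.1% | 5.5% | 5.0% | 4.5% |
| 0.9 | 5.8% | 5.5% | 5.2% | 5.0% | 4.7% |
| 1.0 | 5.0% | 5.0% | 5.0% | 5.0% | 5.0% |
| 1.2 | 3.7% | 4.2% | 4.6% | 5.0% | 5.5% |

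**4. Simulation.** An ANCOVA with a baseline covariate (4,000 runs, ratio 0.7) gave pooled error of 8.0%, 6.6% and 6.1% at placebo n 60, 80 and 100, against 4.9%, 4.9% and 5.2% with HC3. With equal variances at n = 80 the rates were 4.8% and 4.6%. In two-sample simulations (20,000 runs per setting), the unequal-variance test stayed between 4.7% and 5.2% throughout. The planned MMRM with missing data was not simulated.

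**5. Would the lead results change?** Using the true SE, the least favourable cell with n 60 to 100 is ratio 1.2 at n = 60. For mNIS+7 the SE is 2.88 and z = 15/2.88 = 5.2. For Norfolk the SE is 2.88 × 19.2/17 = 3.25 and z = 15.5/3.25 = 4.8. Both remain far above 1.96.

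**6. Do the planned analyses cover it?** The complete-case ANCOVA (4.4.1.3) has the same form. The post-local-treatment, propensity-score and per-protocol analyses (4.4.2.1, 4.4.2.2, 4.4.2.5) reuse that ANCOVA and the MMRM. The pattern-mixture analysis (4.4.2.3) ends in the primary ANCOVA/MI model. The binary analysis (4.4.2.4) uses no residual variance but addresses a different endpoint.

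**The case against.** The strongest reply is that both conditions for an error are unseen. Without the placebo n and a vutrisiran SD, nobody can say from the SAP that standard errors are too small. That stands, and it limits the point to a conditional one.

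A reader might infer unequal spread from the planned means, with placebo worsening by 15 points and vutrisiran staying at 0. A mean of 0 is compatible with any SD, so the documents do not support that inference. Moreover, 17 and 19.2 are SDs of raw change, while the models depend on residual SDs after covariate adjustment.

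It can also be said that spread caused by progression on placebo belongs to the alternative, not to the null under which type I error is calculated. That is fair for that mechanism. However, the null in Section 1.3 concerns a zero difference only, so differences between trials could still make variances unequal under it. Interval coverage is also at stake when the treatment works.

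The arithmetic leaves out covariates, imputation and repeated measures. Imputation by group brings some group-specific spread into the between-imputation variance, but the within-imputation part stays pooled. Finally, the quoted MMRM sentence does not itself say that the matrix is common; this follows from the absence of any grouping.

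**Conclusion.** The point holds as a conditional weakness that is cheap to remove. The models assume equal residual (co)variance across two unlinked groups, give no reason for it, and plan no check. Under the stated assumptions the true error lies between about 3.7% and 8.1%, with no effect at equal n or equal SDs. If placebo is the larger group, the direction reverses.

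Two stronger readings go too far. The documents do not show that the 0.05 familywise rate is exceeded: the error may be nil or conservative. Nor do they suggest that the lead results are fragile: the planned mNIS+7 and Norfolk effects remain clearly significant. The gain is correctly sized intervals throughout, and dependable error control for 10-MWT, mBMI and R-ODS, for which the SAP states no planned effect.

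**What to change.** - **MMRM:** let the covariance matrix differ by treatment group, for example unstructured with GROUP=treatment and Satterthwaite degrees of freedom. Put the pooled unstructured matrix first in the fallback sequence, before Toeplitz, autoregressive and compound symmetry.
- **ANCOVA in each imputed dataset:** use a group-specific residual variance or an HC3 standard error, then combine as planned.
- **At minimum:** prespecify these as a sensitivity analysis for the placebo comparisons.

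The cost is small. With two visits, an unstructured matrix has two variances and one covariance, so separate matrices need six parameters instead of three; the ANCOVA needs one extra variance, or none with HC3. There is a small loss of degrees of freedom. In the simulations above, error stayed near 5% when variances were equal.

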4.4.1.3. ANCOVA

ANCOVA, without incorporating MI, will be the default Month 9 sensitivity and subgroup analyses unless otherwise specified. Patients who complete both baseline and Month 9 will be included in the analysis. For most endpoints, the ANCOVA will include a covariate (baseline value), and factors (treatment group; genotype; age of disease onset; baseline NIS score [<50 vs ≥ 50]), unless otherwise specified. For NIS-related endpoints, the categorical baseline NIS score will not be included in the model.

4.4.2. Primary Efficacy Evaluations

The primary endpoint is change from baseline at Month 9 for mNIS+7 (Section 9.1.1). The primary comparison will be conducted at Month 9. The primary endpoint will be analyzed using the general ANCOVA/MI methods.

Additionally, change from baseline at Month 18 for mNIS+7 will be analyzed as a secondary endpoint using the general MMRM methods.

4.4.2.1. Sensitivity Analysis: Including Data Post Local Standard Treatment for hATTR amyloidosis or Post Serious COVID-19 AE

The primary analysis will not include assessments performed after the initiation of local standard treatment for hATTR amyloidosis or on or after onset of a serious COVID-19 AE (Section 3.5). Sensitivity analysis of mNIS+7 change from baseline including data post local standard treatment for hATTR amyloidosis or post serious COVID-19 AE from either study will be conducted using the ANCOVA method at Month 9 and MMRM method at Month 18.

4.4.2.2. Sensitivity Analysis: Propensity Score

To allow some control of more factors and covariates without saturating the model, a propensity score approach will be used to reduce the predictors to a single propensity score. The propensity score is defined as the probability of being treated with vutrisiran as obtained from a logistic

regression model of treatment group [vutrisiran; placebo (APOLLO)]. The logistic regression model will include the following baseline variables:

- Continuous variables
 - NT-proBNP (log-transformed)
 - mNIS+7
 - Norfolk QoL-DN total score
- Categorical variables
 - Previous tetramer stabilizer use (tafamidis/diflunisal) [Yes; No]
 - Karnofsky Performance Status (KPS) [60; 70-80; 90-100]
 - Cardiac Subpopulation [Yes; No]
 - PND score [I; II; IIIA; IIIB/IV]
 - Age at hATTR Symptom onset [< 50 ; ≥ 50]
 - Neuropathy Impairment Score (NIS) [< 50 ; ≥ 50]
 - Genotype [V30M; non-V30M]
 - FAP stage [I; II/III]

The primary endpoint will be analyzed in this sensitivity analysis using the [ANCOVA](#) method at Month 9 and [MMRM](#) method at Month 18, including the propensity score covariate in addition to the default model factors and covariates.

4.4.2.3. Sensitivity Analysis: Pattern-Mixture Model

The primary analysis [ANCOVA/MI](#) method addresses data under missing at random (MAR) assumptions. To assess the robustness of the primary analysis results under missing not at random (MNAR) assumptions, a sensitivity analysis using a pattern-mixture model (PMM) will be conducted at Months 9 and 18 using a modified [ANCOVA/MI](#) method.

The model will be based on the following assumptions:

1. Patients who have missing data due to COVID-19, including patients who have missing assessments, who have data censored because a serious COVID-19 AE was reported before Month 9 (or 18), or who die due to COVID-19:
 - a. Under the hypothetical estimand of interest where the COVID-19 pandemic did not occur, these assessments should have been obtained with no COVID-19 impact. Therefore, for patients meeting either of these criteria, assessments will be considered MAR, and will be imputed using MI estimated from all nonmissing data collected on treatment from the vutrisiran group.
2. Patients who have missing data unrelated to COVID-19 and are alive before Month 9 (or 18):
 - a. Placebo-treated patients who have missing data: The missing data are considered MAR and will be imputed using MI estimated from placebo-treated patients. The

- imputation is done regardless of whether a patient was on-treatment or discontinued treatment before the scheduled Month 9 (or 18) efficacy assessment.
- b. Vutrisiran-treated patients who have missing data while on treatment: Patients are expected to continue to show benefit from treatment similar to that observed at the scheduled time point. Therefore, missing data during the on-treatment period (within 126 days of the patient's last dose before the scheduled Month 9 [or 18] efficacy assessment) are considered MAR and will be imputed using MI estimated from all nonmissing data collected on treatment from the vutrisiran group. The 126-day window was selected given the long PD effect of vutrisiran.
 - c. Vutrisiran-treated patients who have missing data after stopping their study treatment: Patients will no longer benefit from treatment in the future and will have trajectory similar to placebo-treated patients. Therefore, missing data after treatment discontinuation (more than 126 days after the patient's last dose of study drug before the scheduled Month 9 (or 18) efficacy assessment) will be imputed using the data from placebo-treated patients.
3. Patients who have missing data and who die before Month 9 (or 18) unrelated to COVID-19:
 - a. Assuming deaths observed in the study will likely be related to worsening of disease, the missing data will be imputed by taking random samples from the worst 10% mNIS+7 change from baseline scores among vutrisiran- and placebo-treated patients at Month 9 (or 18). The imputation will be done for patients from both vutrisiran and placebo groups.

Following the procedure describe above, 100 imputed datasets will be generated, and each imputed dataset will be analyzed and estimates combined following the same [ANCOVA/MI](#) model as the primary analysis.

More details on the implementation of PMM are discussed in [Section 9.2](#).

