2. PATIENT POPULATIONS

The following patient populations will be evaluated and used for presentation and analysis of the data in this study, and for applicable analyses, relevant data from the APOLLO study.

- Modified Intent-to-Treat (mITT) Population: All randomized patients who received any amount of study drug. Patients will be analyzed according to the treatment to which they were randomized.
- TTR Per-protocol (PP) Population: All mITT population patients with a nonmissing TTR assessment at baseline and ≥ 1 trough TTR assessment between Months 6 (Week 24) and Month 18 [Week 72]) that meets the requirements described in [Table 3](#). Patients will be analyzed according to the treatment to which they were randomized.
- Month 9 Efficacy PP Population: All mITT population patients treated with vutrisiran or placebo meeting the following criteria:
 - Month 9 efficacy visit date within 3 calendar months of protocol-planned Month 9 efficacy visit window
 - No serious or severe COVID-19 custom query AE terms reported on or before Month 9 efficacy visit date
 - For vutrisiran-treated patients, received all planned vutrisiran doses up to and including Week 36 with ≤ 28 day delay

Patients will be analyzed according to the treatment to which they were randomized.

- Month 18 Efficacy PP Population: All mITT population patients treated with vutrisiran or placebo meeting the following criteria:
 - Month 18 efficacy visit date within 3 calendar months of protocol-planned Month 18 efficacy visit window
 - No serious or severe COVID-19 custom query AE terms reported on or before Month 18 efficacy visit date
 - For vutrisiran-treated patients, received all planned vutrisiran doses up to and including Week 72 with ≤ 28 day delay

Patients will be analyzed according to the treatment to which they were randomized.

- Cardiac Subpopulation: All mITT population patients who had preexisting evidence of cardiac amyloid involvement, defined as patients with baseline left ventricular (LV) wall thickness ≥ 1.3 cm and no aortic valve disease or hypertension in medical history. Patients will be analyzed according to the treatment to which they were randomized.
- Safety Population: All patients who received any amount of study drug. Patients will be analyzed according to the treatment received.
- Pharmacokinetic (PK) Population: All randomized patients who received at least one full dose of study drug and have at least 1 postdose blood sample for PK parameters

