3.5.2. Onset of Serious COVID-19 Adverse Events

Patients who experience a serious COVID-19 AE may have worsening in general health and wellbeing unassociated with the natural course of hATTR amyloidosis or with study drug. Assessments will be censored on or after the onset of a serious COVID-19 AE for all analyses of mNIS+7, Norfolk QoL-DN, 10-MWT, mBMI, and R-ODS, and any associated component/domain scores. This will reflect a hypothetical estimand of interest where the COVID-19 pandemic did not occur, as was the case for placebo group from the APOLLO study.

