4.4.2.5. Other Analysis: Efficacy PP Population

To mitigate for the impact of the COVID-19 pandemic, mNIS+7 will also be analyzed using the Efficacy PP population; full details are provided in [Section 4.9.2](#).

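### In the pattern-mixture analysis, a vutrisiran patient already off drug for a non-COVID reason is imputed as on treatment if the missing value is COVID-related

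*SAP*

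**What the plan says.** Section 4.4.2.3 of the SAP (Amendment 3) describes the pattern-mixture model as the check on the primary analysis under missing-not-at-random assumptions, at Months 9 and 18. It sorts missing values into three groups.

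- **Rule 1** covers "Patients who have missing data due to COVID-19, including patients who have missing assessments, who have data censored because a serious COVID-19 AE was reported" by the time point, together with COVID-19 deaths. For all of them, "assessments will be considered MAR, and will be imputed using MI estimated from all nonmissing data collected on treatment from the vutrisiran group". The reason given is the hypothetical no-pandemic estimand.
- **Rule 2** covers "Patients who have missing data unrelated to COVID-19 and are alive before Month 9 (or 18"). Within it, 2a imputes placebo patients from placebo. Rule 2b imputes vutrisiran patients within 126 days of their last dose from on-treatment vutrisiran data. Rule 2c imputes vutrisiran patients beyond 126 days from placebo data, because "Patients will no longer benefit from treatment in the future and will have trajectory similar to placebo-treated patients".
- **Rule 3** imputes non-COVID deaths in either group from the worst 10% of change scores.

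Section 3.5.2 states the estimand: a "hypothetical estimand of interest where the COVID-19 pandemic did not occur, as was the case for placebo group from the APOLLO study".

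**The concern.** The only test of whether a patient is on or off drug is the 126-day window, and it sits inside rule 2. Rules 1 and 2 exclude each other by the cause of missingness, so a patient in rule 1 never meets that test.

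Take a patient who stops vutrisiran early for an adverse event or lack of effect, stays in the study, and then misses the efficacy visit because of the pandemic or has a serious COVID-19 event. The plan imputes a treated outcome. Had the same patient missed the visit for any other reason, the plan would impute a placebo outcome. Taking away the pandemic gives this patient back the visit but does not put the patient back on drug.

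By Section 3.5.2 the APOLLO placebo group was not exposed to the pandemic, so the rule can act only in the vutrisiran arm and only in its favour. It does so inside the analysis meant to put pressure on the vutrisiran result. By the amendment history (Section 10.3), the Month 18 model was added to support the EU primary endpoint, so the check serves the primary endpoints of both regional testing schemes.

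**Working it through.** **1. Which patients rule 1 changes.** Compare rule 1 with what rule 2 would do for a living vutrisiran patient with a COVID-related missing value.

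| Status at the scheduled assessment | Rule 1 source | Rule 2 source | Consistent with the no-pandemic estimand |
|---|---|---|---|
| Within 126 days of last dose | On-treatment vutrisiran | On-treatment vutrisiran (2b) | Both; no difference |
| Over 126 days, stopped because of COVID-19 | On-treatment vutrisiran | Placebo (2c) | Rule 1 |
| Over 126 days, stopped for another reason | On-treatment vutrisiran | Placebo (2c) | Rule 2c |

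Rule 1 is right for the second row and wrong for the third. Only the third row is at issue.

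**2. How early the patient must have stopped.** Assume doses every 12 weeks from Day 1 and the scheduled assessments at Week 36 (Day 253) and Week 72 (Day 505).

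- Month 9: last dose at Week 24 (Day 169) gives 253 − 169 = 84 days, on drug. Last dose at Week 12 (Day 85) gives 253 − 85 = 168 days, off drug.
- Month 18: last dose at Week 60 (Day 421) gives 505 − 421 = 84 days, on drug. Last dose at Week 48 (Day 337) gives 505 − 337 = 168 days, off drug.

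So the patients concerned had their last dose at Week 12 or earlier (Month 9) or Week 48 or earlier (Month 18), and then have a COVID-related missing value.

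**3. The plan's own figure.** Section 1.4 gives about 160 patients at 3:1, so 160 × 3/4 = 120 on vutrisiran. It gives an mNIS+7 change at 9 months of 15 (SD 17) on placebo against 0 on vutrisiran, and power above 90% with a two-sided t-test at 0.05. The SAP does not state the APOLLO placebo number. With 120 vutrisiran patients, power exceeds 90% for any placebo number of 16 or more (95.2% at 20, 99.8% at 40). For Norfolk QoL-DN (11.5 against −4, SD 19.2) it does so from 19 up. The stated power is reproduced.

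**4. Size of the misrouting.** For k such patients, the shift in the vutrisiran mean is k × (placebo mean − vutrisiran mean)/120.

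- mNIS+7, per patient: (15 − 0)/120 = 0.125 points, or 0.125/15 = 0.83% of the planned difference.
- Norfolk QoL-DN, per patient: (11.5 + 4)/120 = 0.129 points.

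The SAP gives no basis for k, so a range is shown.

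| k | mNIS+7 shift | Difference left | Power, assumed placebo n = 40 | Power, assumed placebo n = 20 |
|---|---|---|---|---|
| 0 | 0 | 15 | 99.8% | 95.2% |
| 5 | 0.625 | 14.375 | 99.6% | 93.5% |
| 10 | 1.25 | 13.75 | 99.3% | 91.4% |
| 20 | 2.5 | 12.5 | 98.0% | 85.6% |

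Power here only gives a sense of scale, since the pattern-mixture analysis is not itself powered. It falls below 90% at about 40 such patients with a placebo n of 40, and at 13 with a placebo n of 20.

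**The case against.** **The group is small.** A patient must be both long off drug and COVID-missing. Visits delayed by COVID-19 are accepted up to six months late (Section 3.7), which shrinks the group further. Off-drug values missing for other reasons still go to 2c, non-COVID deaths still go to the worst 10%, and off-drug values that were observed are kept (Section 3.6) unless a censoring rule applies. All of this stands, and it limits the size of the problem.

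**The primary analysis also imputes within arm.** It might be said that the model merely fails to add pressure for these patients. At Month 9 it does worse than that. The primary multiple imputation is fitted to all vutrisiran data, including values after discontinuation, whereas rule 1 uses on-treatment data only. For this patient the stress test can be kinder than the analysis it tests.

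**Section 9.2 is largely redacted.** A treatment-status flag could sit there. That cannot be excluded, but it cannot be assumed to override a visible rule that states no such condition.

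**Stronger readings.** A reader might infer that all the plan's COVID-related checks discard vutrisiran failures. They do not. The pattern-mixture model removes nobody, and Section 4.4.2.1 adds back data after a serious COVID-19 event with no dosing filter.

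A reader might also see the same defect in the Efficacy PP population. Section 4.4.2.5 presents it as COVID mitigation ("To mitigate for the impact of the COVID-19 pandemic, mNIS+7 will also be analyzed using the Efficacy PP population"), yet the Month 9 criterion in Section 2 is all-cause and applies to one arm: "For vutrisiran-treated patients, received all planned vutrisiran doses up to and including Week 36", with at most 28 days' delay. That mismatch is real. However, a dosing requirement is an ordinary compliance criterion, the analysis is listed as another analysis rather than a sensitivity analysis, and a late dose is not necessarily an efficacy failure. The documents give no figures from which to size any bias.

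**Conclusion.** The point holds for the pattern-mixture model. Rule 1 as written imputes a treated outcome for patients whom rule 2c, and the no-pandemic estimand, would treat as off drug. The error runs in one direction.

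Its size is at most about 0.125 mNIS+7 points in the vutrisiran mean per affected patient. This rests on the Month 9 planning means of 15 and 0 and on 120 vutrisiran patients. It is an upper figure, because it gives full placebo worsening to someone who was dosed for part of the period. The SAP has no planning means for Month 18, so no figure is offered there.

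Nothing here supports the inference that the primary result is biased or would be overturned: the rule belongs to a sensitivity analysis outside the testing hierarchy. What it affects is how much reassurance that analysis can give. The Efficacy PP dosing criterion is a secondary matter of choice.

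**What to change.** In Section 4.4.2.3, limit rule 1 for vutrisiran patients to those who were within 126 days of their last dose before the scheduled assessment, or who stopped dosing because of COVID-19. Send all other vutrisiran patients with COVID-related missing values to rule 2c. Make the intermediate datasets and imputation steps in Sections 9.2.1 and 9.2.2 agree, and report how many patients fall under each rule.

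The cost is a sentence or two in the rules plus the matching specifications. No new data are needed: discontinuation due to COVID-19 is already tabulated (Section 4.1), and COVID-related dosing changes are already summarised (Section 4.9.1).

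Optionally, restrict the Efficacy PP dosing criterion at both time points to doses missed or delayed because of COVID-19, which would match the set's stated purpose.
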